Study Responsible Clinician	<hr/> 
See Electronic Signature Report [name], OD Principal Research Optometrist
	<hr/> 
DATE

Clinical Operations Manager	<hr/> 
See Electronic Signature Report [REDACTED] Clinical Operations Department
	<hr/> 
DATE

Biostatistician	<hr/> 
See Electronic Signature Report [REDACTED] Biostatistician II, Clinical Sciences
	<hr/> 
DATE

Biostatistics Reviewer	<hr/> 
See Electronic Signature Report [REDACTED]. Senior Manager of Biostatistics, Clinical Sciences
	<hr/> 
DATE

Data Management	<hr/> 
See Electronic Signature Report [REDACTED] Clinical Project Manager – Data & Systems, Clinical Operations
	<hr/> 
DATE

Approver:	<hr/> 
See Electronic Signature Report [REDACTED] Director of Global Medical Affairs
	<hr/> 
DATE

CHANGE HISTORY

Version	Originator	Description of Change(s) and Section Number(s) Affected	Date
1.0	[name] & [name]	Original Protocol	01 OCT 2018
2.0	[name]	
Clarification for treatment of Bruder MaskUpdate to Section 2.2Topography added to Table 3	15 NOV 2018

[figure not shown]
SYNOPSIS

Protocol Title	MiBo ThermoFlo Lid Temperature Evaluation
Sponsor	JJVC, [name]
Clinical Phase	Phase 4
Trial Registration	This study will be registered on ClinicalTrials.gov by the Sponsor
Test Article(s)	Investigational Product: MiBo ThermoFlo Control Product: Bruder Moist Heat Single Eye Compress
Wear and Replacement Schedules	N/A
Objectives	
Determine anterior and posterior eyelid temperature after use of the MiBo ThermoFlo following standard clinical protocol and evaluate changes to the tear film with one MiBo ThermoFlo treatment session.
 
Primary Objective: Determine the temperature of the palpebral conjunctiva after MiBo ThermoFlo treatment and Bruder Mask (i.e. hot compress) treatment using the ICI-7320 infrared camera (Infrared Cameras Inc., Beaumont, TX)
 
Secondary Objectives: Tear Film Lipid Layer Thickness and Non-Invasive Tear Break Up Time post treatment

Study Endpoints	
Primary endpoint(s): Palpebral Conjunctival Temperature
 
Secondary endpoint(s): Tear Film Lipid Layer Thickness, Non-invasive tear break up time (NITBUT)

Study Design	
This study is a prospective, contralateral, single-site, single-visit unmasked evaluation of external and internal eyelid temperature after treatment with the MiBo ThermoFlo. Approximately 20 subjects will be evaluated for enrollment in the study, with a goal of a minimum of 12 subjects completed. Subjects will be randomly assigned to receive 12 minutes of MiBo ThermoFlo treatment (treatment) on 1 eye and 10 minutes of Bruder mask treatment (control) on the fellow eye.
 
See the flow chart at the end of the synopsis table for the schematic of the study visits and procedures of main observations (Figure 1).

Sample Size	Up to 20 subjects will be enrolled with a goal of a minimum of target of 12 subjects to complete
Study Duration	The study will last approximately 1.5 months and include a 1-month enrollment period
Anticipated Study Population	Individuals between the ages of 18-80 years old (inclusive) with less than grade 3 partial Meibomian glands on the Pult 5-point grading scale.

Eligibility Criteria	
Potential subjects must satisfy all the following criteria to be enrolled in the study:
 
1.1. Inclusion Criteria
 
Potential subjects must satisfy all the following criteria to be enrolled in the study:
 
 1. The subject must read, understand, and sign the STATEMENT OF INFORMED CONSENT and receive a fully executed copy of the form 2. Appear able and willing to adhere to the instructions set forth in this clinical protocol 3. Between 18 and 80 (inclusive) years of age at the time of screening 4. Subjects must possess a functional/usable pair of spectacles and bring them to the visit (only if applicable - to the investigators discretion) 
Potential subjects who meet any of the following criteria will be excluded from participating in the study:
 
 1. Currently pregnant or lactating 2. Any systemic disease (e.g., Sjögren's Syndrome), allergies, infectious disease (e.g., hepatitis, tuberculosis), contagious immunosuppressive diseases (e.g., HIV), autoimmune disease (e.g. rheumatoid arthritis), or other diseases, by self-report, which are known to interfere with participation in the study 3. Clinically significant (Grade 3 or 4 on the FDA classification scale) slit lamp findings (e.g. corneal edema, neovascularization or staining, tarsal abnormalities or bulbar injection) 4. Grade 3-4 Percentage of Partial Meibomian Glands on the Pult 5-point grading scale 5. Significant conjunctivitis (Grade 3 or greater) 6. Active Ocular Infection or Inflammation (Grade 3 or greater) 7. Any history of eyelid surgery or abnormality 8. History of Metal Implants in the Eyelids 9. Any known hypersensitivity or allergic reaction to ultrasound coupling gel 10. LASIK Surgery within 2 weeks of the Baseline Visit 11. Participation in any contact lens or lens care product clinical trial within 14 days prior to study enrollment 12. History of MiBo ThermoFlo or Lipiflow treatment Within the Last 6 months 13. Employee or immediate family member of an employee of clinical site (e.g., Investigator, Coordinator, Technician)
----------------------	---

Disallowed Medications/Interventions	History of MiBo ThermoFlo or Lipiflow treatment within the last 6 months
Measurements and Procedures	ICI-7320 infrared camera (Infrared Cameras Inc., Beaumont, TX) Tear Film Lipid Layer (Lipiview) Non-invasive Tear Break Up Time
Microbiology or Other Laboratory Testing	None
Study Termination	The occurrence of one or more Unanticipated Adverse Device Effect (UADE), or any SAE where relationship to study agent cannot be ruled out, will result in stopping further dispensing investigational product. In the event of a UADE or SAE, the Sponsor Medical Monitor may unmask the treatment regimen of subject(s) and may discuss this with the Principal Investigator before any further subjects are enrolled.
Ancillary Supplies/ Study-Specific Materials	Aquasonic 100 Ultrasound Transmission Gel, Bruder Moist Heat Single Eye Compress
Principal Investigator(s) and Study Institution(s)/Site(s)	A full list of Principal Investigators, clinical sites, and institutions is kept separately from the Study Protocol and is included in the study Trial Master File.

Figure 1: Study Flowchart

COMMONLY USED ABBREVIATIONS AND DEFINITIONS OF TERMS

ADD	Plus Power Required For Near Use
ADE	Adverse Device Effect
AE	Adverse Event/Adverse Experience
BCVA	Best Corrected Visual Acuity
BSCVA	Best Spectacle Corrected Visual Acuity
CFR	Code of Federal Regulations
CLUE	Contact Lens User Experience
COAS	Complete Ophthalmic Analysis System
COM	Clinical Operations Manager
CRA	Clinical Research Associate
CRF	Case Report Form
CRO	Contract Research Organization
CT	Center Thickness
■■■■■	■■■■■
D	Diopter
DMC	Data Monitoring Committee
eCRF	Electronic Case Report Form
EDC	Electronic Data Capture
ETDRS	Early Treatment Diabetic Retinopathy Study
FDA	Food and Drug Administration
GCP	Good Clinical Practice
HIPAA	Health Insurance Portability and Accountability Act
IB	Investigator's Brochure
ICF	Informed Consent Form
ICH	International Conference on Harmonization
IDE	Investigational Device Exemption
IEC	Independent Ethics Committee
IRB	Institutional Review Board
ISO	International Organization for Standardization
ITT	Intent-to-Treat
JJVC	Johnson & Johnson Vision Care, Inc.
LC	Limbus Center
LogMAR	Logarithm of Minimal Angle of Resolution
MedDRA [®]	Medical Dictionary for Regulatory Activities
MGD	Meibomian Gland Dysfunction
MOP	Manual of Procedures
NIH	National Institutes of Health
OD	Right Eye
OHRP	Office for Human Research Protections
OHSR	Office for Human Subjects Research
OS	Left Eye
OU	Both Eyes
PD	Protocol Deviation
PHI	Protected Health Information
PI	Principal Investigator

PIG	Patient Instruction Guide
PQC	Product Quality Complaint
PRO	Patient Reported Outcome
QA	Quality Assurance
QC	Quality Control
SAE	Serious Adverse Event/Serious Adverse Experience
SAP	Statistical Analysis Plan
SAS	Statistical Analysis System
SD	Standard Deviation
SOP	Standard Operating Procedure
UADE	Unanticipated Adverse Device Effect
USADE	Unanticipated Serious Adverse Device Effect
VA	Visual Acuity

1. INTRODUCTION AND BACKGROUND

Several approaches have been used to treat Meibomian Gland Disease (MGD), including physical expression of the Meibomian glands alone or in conjunction with the use of various devices to heat the eyelids. The methods used to heat the eyelid tissue, colloquially referred to as hot compresses, include using hot water soaked cloths, exothermic chemical reactions (EyeGeine Wafers), heated flax seeds (MGDRx), heated rice, and proprietary bead technology (e.g. Bruder MediBeads).⁴⁻⁷ Reports in the scientific literature indicate that for effective liquefaction of meibum in eyes with Meibomian Gland Dysfunction (MGD), a minimum temperature of approximately 40°C must be reached at the inner eyelid. Traditional treatments for MGD fail to reach this internal eyelid temperature, while therapy that applies sufficient heat to the inner eyelid surface can reach this temperature threshold.⁶

One device that attempts to liquefy inspissated meibum in patients with MGD is the MiBo ThermoFlo. The MiBo ThermoFlo uses a thermoelectric probe coupled to the eyelid using ultrasound transmission gel after a system initiation/warm up period that heats a silver eye pad to a temperature of approximately 42°C. Upon starting treatment, the MiBo ThermoFlo eye pad is moved along the eyelid surface using a gentle circular motion, combining eyelid massage with controlled heat to the eyelid. Per the manufacturer, typical treatment duration ranges from 5 minutes to 12 minutes per session, with 3 treatment sessions over 2 weeks recommended to obtain maximum therapeutic effect (<http://www.mibomedicalgroup.com/miboThermoFlo.html>). Using the MiBo ThermoFlo Elite Eye Pad, upper and lower eyelids can be treated simultaneously.

Previous pilot data (TearScience; JJVC Confidential) suggests that treatment with the MiBo ThermoFlo does not adequately raise Meibomian gland temperature at the inner eyelids to therapeutic levels. This study will evaluate inner and outer eyelid temperature obtained with use of the MiBo ThermoFlo, as well as look at changes in the tear film after 1 treatment session. Temperature will be measured via thermography (see SOP_C31_Thermography_v1.0).

1.2. Name and Descriptions of Investigational Products

This study will evaluate the MiBo ThermoFlo, a therapeutic medical device for dry eye therapy. It uses a proprietary thermoelectric heat pump to help liquefaction of meibum in the Meibomian glands. The contralateral control article is the Bruder Moist Heat Eye Compresses. The Bruder mask uses MediBead technology, which absorbs water from the air and stores it inside the beads. When microwaved, the absorbed water is released as moist heat.

1.3. Intended Use of Investigational Products

The intended use of the MiBo ThermoFlo is the treatment of chronic dry eye by heating inspissated Meibomian glands, combined with gentle lid massage. Subjects will receive 12 minutes of treatment. The Bruder Moist Heat Eye Compresses is intended for the treatment of chronic dry eye and MGD and will be applied for 10 minutes.

1.4. Summary of Findings from Nonclinical Studies

Not Applicable – Marketed product only.

1.5. Summary of Known Risks and Benefits to Human Subjects

The risks of treatment with the MiBo Lipiflow are minimal. These risks include discomfort or sensation of pressure on the eyelids related to the procedure or irritation secondary to use of ultrasound coupling gel. These risks are self-limiting and typically resolve without treatment.

The risk of thermal burn with normal use of the MiBo Lipiflow or the Bruder mask is minimal. The temperature of the MiBo ThermoFlo treatment paddle is 108 degrees Fahrenheit (42 degrees Celsius), under the temperature required to cause a thermal burn with prolonged exposure to heat. The Bruder mask utilizes proprietary beads heated using a microwave oven to provide heat to the eyelid surface. The instructions for use limit the heating time to 20 seconds, with 2 additional 5 second heating sessions (maximum 30 seconds total) to achieve the required treatment temperature. Subjects will be educated to inform the study personnel if the device becomes too warm or if the treatment becomes painful.

The benefit to either treatment is that the surface heating treatments of the eyelid and Meibomian glands may lead to increase of available lipid to the tear film. This could transiently increase the thickness of the tear lipid layer or transiently increase tear break up time.

2. STUDY OBJECTIVES, ENDPOINTS AND HYPOTHESES

2.1. Objectives

The primary study objective of this pilot study is to measure posterior eyelid temperature (palpebral conjunctiva) to determine the ability of the MiBo ThermoFlo to raise posterior eyelid temperature to levels sufficient to provide a therapeutic effect in the treatment of MGD.

Other observations in this study include testing whether the MiBo ThermoFlo treatment can induce a change in tear lipid layer thickness and/or non-invasive tear break up time after (1) 12-minute treatment session.

2.2. Endpoints

The primary study endpoint is posterior eyelid temperature (palpebral conjunctiva) using the ICI-7320 infrared camera (Infrared Cameras Inc., Beaumont, TX). This metric has been selected as the ICI-7320 is FDA-approved [510(k) clearance] for use in medical imaging of any part of the body's surface. Collection of surface temperature with infrared video will allow for capture of the inner eyelid temperature while eyelids are inverted to access the palpebral conjunctiva. Other observations endpoints are Topography, Tear Lipid Layer thickness and Non-invasive Tear Break Up Time after treatment.

2.3. Hypotheses

1. After 12 minutes of treatment, the MiBo ThermoFlo will not heat the posterior eyelid palpebral conjunctiva to a temperature of 40°C.

Background: Ocular surface temperature is usually 34.03 ± 0.51 °C in the ‘normal’ eye. The temperature required to melt obstructive secretions in the Meibomian glands ranges from 32-45°C but the more severely obstructed glands present in MGD would require a temperature of >40°C, for effective treatment. There is an approximate 5°C difference in temperature between heat applied on the external eyelid surfaces and that which reaches the inner surface of the lids (palpebral conjunctiva), where the meibomian glands are located. This difference is due to both dissipation of heat while passing through the lid tissues and to constant movement of blood through vasculature wicking heat away from the lids. Therefore, achieving the desired temperature of 40°C at the palpebral conjunctiva requires a constant heat of at least 45°C be maintained on the outer lid surface, a temperature which may be both uncomfortable and risk causing thermal injury to the eyelid skin.

Other Observations

1. After 10 minutes of treatment, the Bruder Mask will not heat the posterior eyelid palpebral conjunctiva to a temperature of greater than 40°C.
2. There is no difference in posterior eyelid palpebral conjunctiva between the Bruder Mask and the MiBo ThermoFlo

3. TARGETED STUDY POPULATION

3.1. General Characteristics

The study population are individuals between the ages of 18 to 80 years old (inclusive) with sufficient Meibomian gland anatomy to qualify for MiBo ThermoFlo treatment. This is defined as having Grade 0-2 Percentage of Partial Meibomian Glands on the Pult 5-point grading scale. Subjects with Grade 3-4 Percentage of Partial Meibomian Glands will be excluded.

3.2. Inclusion Criteria

Potential subjects must satisfy all the following criteria to be enrolled in the study:

1. The subject must read, understand, and sign the STATEMENT OF INFORMED CONSENT and receive a fully executed copy of the form
2. Appear able and willing to adhere to the instructions set forth in this clinical protocol
3. Between 18 and 80 (inclusive) years of age at the time of screening
4. Subjects must possess a functional/usable pair of spectacles and bring them to the visit (only if applicable - to the investigators discretion)

3.3. Exclusion Criteria

Potential subjects who meet any of the following criteria will be excluded from participating in the study:

Exclusion Criteria after Screening and Baseline:

1. Currently pregnant or breastfeeding
2. Any systemic disease (e.g., Sjögren's Syndrome), allergies, infectious disease (e.g., hepatitis, tuberculosis), contagious immunosuppressive diseases (e.g., HIV), autoimmune disease (e.g. rheumatoid arthritis), or other diseases, by self-report, which are known to interfere with participation in the study
3. Clinically significant (Grade 3 or 4 on the FDA classification scale) slit lamp findings (e.g. corneal edema, neovascularization or staining, tarsal abnormalities or bulbar injection)
4. Grade 3-4 Percentage of Partial Meibomian Glands on the Pult 5-point grading scale
5. Giant Papillary Conjunctivitis (Grade 3 or greater)
6. Active Ocular Infection or Inflammation (Grade 3 or greater)
7. Any history of eyelid surgery or abnormality
8. History of Metal Implants in the Eyelids

9. Any known hypersensitivity or allergic reaction to ultrasound coupling gel
10. LASIK Surgery within 2 weeks of the Baseline Visit
11. Participation in any contact lens or lens care product clinical trial within 14 days prior to study enrollment
12. History of MiBo ThermoFlo or Lipiflow treatment Within the Last 6 months
13. Employee or immediate family member of an employee of clinical site (e.g., Investigator, Coordinator, Technician)

3.4. Enrollment Strategy

Study subjects will be recruited from the Institution/clinical site's subject database and/or utilizing Independent Ethics Committee (IEC) or Institutional Review Board (IRB) approved materials.

4. STUDY DESIGN AND RATIONALE

4.1. Description of Study Design

This study is a prospective, contralateral, single-site, single-visit unmasked evaluation of external and internal eyelid temperature after treatment with the MiBo ThermoFlo. Approximately 20 subjects will be evaluated for enrollment in the study, with a goal of a minimum of 12 subjects completed. If a subject meets all eligibility criteria then the subject will be randomly assigned to 1 of 2 treatment sequences in a contralateral fashion, (1) MiBo ThermoFlo (left eye) / Bruder mask (right eye) or (2) Bruder mask (left eye) / MiBo ThermoFLo (right eye). Subjects will undergo each treatment for a period of 12 minutes for the MiBo ThermoFlo and 10 Minutes for the Bruder mask, per the manufacturer recommendations.

The study visit is expected to last approximately 2.5 hours. Subjects will undergo Meibography, tear lipid layer measurements, non-invasive tear break-up time, eyelid photography and the study treatments (MiBo ThermoFlo and Bruder mask).

4.2. Study Design Rationale

Previous work suggests that treatment with the MiBo ThermoFlo does not adequately raise Meibomian gland temperature at the inner eyelids to therapeutic levels therefore, this study explores the ability of the MiBo ThermoFlo to increase posterior eyelid temperature over 1 treatment session. A contralateral design was considered the most efficient design to assess the primary endpoint of the study. Given the nature of the treatment, masking of the investigator and the subjects is not feasible.

4.3. Enrollment Target and Study Duration

The target enrollment is 20 subjects, with a minimum of 12 subjects completing the 1-visit study, which will last for approximately 2.5 hours.

5. TEST ARTICLE ALLOCATION AND MASKING

5.1. Test Article Allocation

A computer-generated randomization scheme will be used to randomly assign subjects, in blocks of 2, to one of the two possible treatment sequences (left eye: MiBo ThermoFlo/ right eye: Bruder mask or right eye: Bruder mask/ left eye: MiBo ThermoFlo). The random scheme will be generated by site using the PROC PLAN procedure from SAS Software Version 9.4 or higher (SAS Institute, Cary, NC).

The study site must follow the randomization scheme provided and complete enrollment according to the randomization list and not pre-select or assign subjects. The randomized assignment of subjects will be performed at the first visit prior to the first fitting. The following must have occurred prior to randomization:

- Informed consent has been obtained
- Subject meets all the inclusion / exclusion criteria
- Subject history and baseline information has been collected.

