5.2. Masking

Given the medical device being evaluated, masking is not possible. As such, this is an unmasked, open label trial. Subjects will be aware of the identity of the investigational product. Investigators and clinical site personnel involved in the data collection will not be masked as to the identity of the investigational product. Given the nature of the treatment, it is unlikely that the lack of masking will affect the study outcomes.

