1.8	Eligibility after Baseline	All responses to Inclusion Criteria questions must be answered “yes” and all responses to Exclusion Criteria questions must be answered “no” for the subject to be considered eligible.	

Visit 1: Baseline			
Step	Procedure	Details	
		If subject is deemed to be ineligible after baseline, proceed to Final Evaluation and complete all forms.	

Visit 1: Treatment			
Step	Procedure	Details	
1.9	Eyelid Photography	The upper and lower eyelid margins of the subject will be photographed, OD, OS	Work Aid: Eyelid Photography
1.10	Tear Lipid Layer Thickness (LLT)	Measure the pre-treatment tear film LLT using the TearScience Lipiview, (OD, OS)	Work Aid: TearScience LipiView II Lipid Layer Thickness Measurement
1.11	Non-Invasive Tear Break Up Time (NITBUT)	Perform pre-treatment NITBUT using Oculus Keratograph 5 (OD, OS)	SOP_C12_Oculus Keratograph_V2
1.12	Corneal Topography	Perform pre-treatment corneal topography with the Oculus Keratograph	SOP_C12_Oculus Keratograph_V2
1.13	Thermography	Perform pre-treatment measurement of the external eyelid and palpebral conjunctival temperature for the upper and lower lids, (OD and OS)	SOP_C31_Thermography_V1.0
1.14	Randomization	Randomize treatment to eye using the randomization schedule	
1.15	MiBo ThermoFlo	Perform 12-minute MiBo ThermoFlo treatment on the eye indicated on the randomization schedule using the ThermoFlo Elite Eye Pad.	Work Aid: MiboFlo
1.16	Thermography	Immediately perform post-treatment measurement of the external eyelid and palpebral conjunctival temperature for the upper and lower lids, collecting data for the lower lid first.	SOP_C31_Thermography_V1.0
1.17	Bruder Mask	Heat the Bruder Mask per the manufacturer's instructions, measure the mask surface temperature and perform 10 minute Bruder Mask treatment on the contralateral eye.	Work Aid: Bruder Mask_V2

Visit 1: Treatment			
Step	Procedure	Details	
		Note: The Bruder Mask should be placed gently on the closed eyelids. Do not apply pressure on the mask and eye.	
1.18	Thermography	Perform post-treatment measurement of the external eyelid and palpebral conjunctival temperature for the upper and lower lids	SOP_C31_Thermography_V1.0
1.19	Tear Lipid Layer Thickness (LLT)	Measure the post-treatment tear film LLT using the TearScience Lipiview, OD, OS	Work Aid: TearScience LipiView II Lipid Layer Thickness Measurement

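### A printed block size of 2 at one unmasked site, with no concealment described, lets staff deduce every second eye assignment before the pre-treatment readings; the consequence is limited and the remedy is cheap

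*Combined protocol and SAP*

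**What the plan says.** Section 4.1 describes a "prospective, contralateral, single-site, single-visit unmasked evaluation" with two mirror-image sequences: MiBo left with Bruder right, or the reverse. Section 5.1 sets the allocation: "A computer-generated randomization scheme will be used to randomly assign subjects, in blocks of 2, to one of the two possible treatment sequences". It tells the site to "complete enrollment according to the randomization list and not pre-select or assign subjects". No envelope, central or EDC release is described. The remark in 5.1 that the scheme is generated by site can be read as one list per site or as a list made by site staff.

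On masking, section 5.2 says: "Investigators and clinical site personnel involved in the data collection will not be masked as to the identity of the investigational product".

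Section 5.1 requires eligibility and baseline information before randomisation. Section 7.2 follows that order and reaches "Randomize treatment to eye using the randomization schedule" only at step 1.14. Before it come slit lamp and Pult grading (1.6, 1.7), the eligibility decision (1.8), lid photographs, LLT, NITBUT and topography (1.9 to 1.12), and thermography of both eyes (1.13).

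The two sequences printed in 5.1 are the same one written twice, both with MiBo on the left eye. They do not match the two distinct sequences in 4.1.

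**The concern.** Collecting baseline data before randomisation protects those data only if the next assignment cannot be foreseen. A block of 2 with two sequences makes the second member of every pair the complement of the first. The site sees each assignment as it is used, and the block size is in the protocol it works from.

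Side is the only randomised element: MiBo is always given first (step 1.15) and Bruder second (step 1.17). Several earlier steps leave the operator discretion for each eye. These include the slit lamp and Pult grades, the placement and size of the thermography zone (thermography SOP, image analysis), and the option to delete and repeat a LipiView recording (LipiView work aid). Two things could then depend on the coming assignment: whether a borderline subject with one worse eye enters, and how each eye is read before treatment.

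**Working it through.** **Inputs.** Block size 2 (5.1); two sequences, 1:1 implied (4.1); one site (4.1); unmasked staff (5.2); randomisation at step 1.14 (7.2); target 20, minimum 12 completing (4.3). The plan states no predictability figure, and 14.2 says no formal sample size calculation was possible, so there is no stated figure to reproduce.

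**1. Predictability.** Take a permuted block with k places for each sequence (size 2k).

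- Expected number fixed by earlier assignments = 2k/(k+1), so the share is 1/(k+1).
- Expected correct guesses, always naming the sequence with more places left = k + ½[4^k / C(2k,k) − 1].

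| Scheme | Certain | Guessed correctly |
|---|---|---|
| Fixed blocks of 2 (k=1) | 1/2 = 50% | 1.5/2 = 75% |
| Fixed blocks of 4 (k=2) | 1/3 = 33.3% | 2.833/4 = 70.8% |
| Fixed blocks of 6 (k=3) | 1/4 = 25% | 4.1/6 = 68.3% |
| One block of 20 (k=10) | 1/11 = 9.1% | 12.34/20 = 61.7% |
| Simple randomisation | 0% | 50% |
| Undisclosed random 4/6 | not computed | about 68% (simulated) |
| Undisclosed random 2/4/6 | not computed | about 69–70% (simulated) |

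Under the plan, 20 × 0.5 = 10 assignments are certain and 20 × 0.75 = 15 are guessed correctly. At 12 subjects the figures are 6 and 9. The first subject of each pair stays at 50/50 unless the list is visible.

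**2. Where foreknowledge could enter the analysis.**

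- Primary contrast (14.5): the fixed effects are sequence, treatment, eyelid location and treatment by location. There is no baseline temperature term, so the step 1.13 readings do not enter it. Selection of asymmetric subjects could. At most half the subjects are predictable with certainty, so a mean between-eye shift of d among those subjects moves the contrast by d/2. The documents give no basis for a value of d.
- MiBo against 40°C (2.3, hypothesis 1): this concerns the MiBo eye alone and does not depend on the allocation of sides.
- LLT and NITBUT: 2.1 frames these as change after treatment, so the pre-treatment readings matter. Sections 14.6 and 14.7 plan no inferential analysis of them.

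**3. Does the sequence term cover left/right imbalance?** Let δ be the left-minus-right temperature difference and τ the treatment effect. The within-subject difference (MiBo minus Bruder) has mean τ + δ when MiBo is on the left and τ − δ when it is on the right. Over n1 and n2 subjects the estimate is centred on τ + δ(n1 − n2)/n. The sequence main effect is constant within a subject and cancels. A side effect is the sequence-by-treatment interaction, which 14.5 does not contain.

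With an assumed δ = 0.5°C, the shift is 0 at 6:6, 0.5 × 6/12 = 0.25°C at 9:3, and 0.5 × 8/20 = 0.20°C at 14:6. A simulation of the 14.5 fixed effects with a random subject intercept and a true effect of 1.0 gave 1.00, 1.25 and 1.20, in agreement. Adding an eye term removed the shift.

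The SD of (n1 − n2)/n, and the resulting shift for an assumed δ of 0.1 to 0.5°C, are:

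- Simple randomisation, n = 20: 1/√20 = 0.22, or 0.02 to 0.11°C.
- Simple randomisation, n = 12: 1/√12 = 0.29, or 0.03 to 0.14°C.
- One block of 20 stopped at 12: variance of n1 = 12 × ½ × ½ × 8/19 = 1.26, SD 1.12; 2 × 1.12/12 = 0.19, or 0.02 to 0.09°C.

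Under simple randomisation a split of 9:3 or worse has probability 14.6% at n = 12, and 14:6 or worse 11.5% at n = 20. Balance therefore does useful work in the model as written, and a replacement scheme should keep most of it.

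**The case against.** The strongest reply is that foreknowledge has little to act on. Every subject gets both treatments, and eligibility is decided per subject: a disqualifying grade excludes the subject whichever eye would receive MiBo. A reader might infer that predictable assignments let staff steer subjects into an arm, as in a parallel-group trial. The design rules that out. Harm through selection needs staff to admit or exclude borderline asymmetric subjects according to side, and needs that asymmetry to affect lid temperature. The documents show neither.

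It can also be said that post-treatment thermography is unmasked under any scheme, with an operator-chosen zone. That is probably the larger route to bias, and changing the blocks does not touch it. A further point is that blocks of 2 protect the contrast against a left/right difference, which unrestricted randomisation under the present model would not.

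All of this stands, and it limits the point without removing it. Masking after treatment may be infeasible, but concealment until step 1.14 is feasible, and 5.2 does not discuss it. The balance argument is a reason to choose a large balanced block and add an eye-side term, rather than to keep blocks of 2.

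**Conclusion.** The point holds as a cheap design improvement. Half the assignments can be deduced with certainty and about three quarters guessed, which undercuts the protocol's own order of baseline before randomisation. This assumes that staff know the printed block size and keep track of earlier assignments. The count of 10 assumes 20 subjects randomised; the share is one half for any even number.

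Two stronger readings are tempting. One is that the site knows every assignment because it holds an open list. The documents refer to a list that the site follows but do not say how assignments are released, so this is possible but not shown. The other is that the primary result is biased through distorted baseline temperatures. The 14.5 model does not use them. What remains exposed is the entry of borderline asymmetric subjects into the MiBo-minus-Bruder contrast, and the pre-treatment LLT and NITBUT readings. No size in °C can be given for either from the documents.

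**What to change.** - **Section 5.1:** replace the blocks of 2 with one balanced block of 20, or another large block size not disclosed to the site. Mixed small blocks alone help little. State that the list is generated and held away from site staff.
- **Section 7.2, step 1.14:** release each assignment only at this step, after the baseline readings are saved, for example from sequentially numbered opaque envelopes. Both changes are needed: envelopes do not hide a known block of 2, and a large block does not help if the list is open.
- **Section 14.5:** add eye side (left/right) as a fixed effect.
- **While rewriting 5.1:** reconcile its two identical sequences with the two distinct ones in 4.1. Taken literally, 5.1 would make every assignment known and leave the eye-side term inestimable.

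The cost is a revised sentence or two, a re-run of PROC PLAN, 20 envelopes and one model term. The downside is a possible small side imbalance if enrolment stops before 20. The eye-side term handles it for one degree of freedom and a small loss of precision. At 7:5, for example, the variance of the contrast rises by the factor n²/(4·n1·n2) = 144/140 = 1.03.
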